3. STUDY DESIGN

The study will be a multicenter, randomized, double-blind trial to evaluate the efficacy of NTZ compared to placebo in treating colds due to EV/RV infection.

Subjects will be randomized 1:1 to one of the following groups:

- Group 1 (NTZ): Two NTZ 300 mg tablets b.i.d. for 5 days
- Group 2 (Placebo): Two placebo tablets b.i.d. for 5 days

Enrollment and the primary efficacy analysis will be stratified by (1) time from onset of illness to study enrollment (0-24, >24-≤36, or >36 hours from onset), (2) pre-enrollment use of symptom relief medication, and (3) presence of underlying lung condition including asthma, COPD, or past or present history of smoking.

This study is expected to run from August 2018 through April 2019.

Rationale for important issues in the study design is described below:

- *Choice of NTZ dose and duration of treatment.* The dose of NTZ used for this clinical trial (600 mg b.i.d. for 5 days) was associated with a reduction of the duration of symptoms and time to ability to perform all normal activities in subjects with EV/RV infection in a previous trial of NTZ for the treatment of influenza (Study RM08-3002). In clinical trials involving 2,886 subjects, adverse events reported by subjects receiving 600 mg NTZ b.i.d. for 5 days were similar to those of subjects receiving the placebo, with the exception of a higher rate of diarrhea (8.1% compared to 5.8% for the placebo). Studies of NTZ at higher doses have shown dose-dependent increases in the frequency of reported diarrhea and other gastrointestinal side effects, therefore no higher dose is planned for this study.
- *Choice of control groups.* A placebo control is appropriate for the study due to lack of any approved active control.
- *Choice of patient population.* The population to be studied includes adults and adolescents at least 12 years of age with EV/RV infection. This is a population similar to those selected for studies RM08-3001, RM08-3002, RM08-3003 and RM08-3004 of the NTZ 300 mg extended release tablets in more than 3,000 subjects with influenza-like illness. No safety concerns have been identified from these clinical trials.

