8. STATISTICAL CONSIDERATIONS

8.1. Sample Size Calculations

The Symptom Response definitions for this study will be derived from the subjects' FLU-PRO questionnaire responses as described in section 8.3 below. The FLU-PRO-derived endpoint is expected to track very closely to return to usual health status (a daily yes/no question in the FLU-PRO questionnaire), which in turn is expected to track very closely to ability to perform 100% of normal activities. We assume, therefore, that the cumulative distributions of time to Symptom Response for the placebo treatment group will closely reflect historical data from Romark Study RM08-3002 for time from first dose until the EV/RV-infected subjects report that they are able to perform 100% of usual activities (see placebo curve in chart below). Then, to calculate sample size, we assume that treatment with NTZ treatment should result in reduction of at least 48 hours in median time to symptom response. The following curves have been developed for determining sample size.

Based upon these curves, a sample size of 530 subjects with laboratory-confirmed EV/RV infection (i.e. 265 for each of the 2 groups) will provide 90% power to detect a statistically significant difference in the survival distributions between the NTZ and placebo groups (2-sided alpha of 0.05). This calculation was performed for the Gehan rank test using SAS PROC POWER (SAS 9.4) with the curves shown above (proportion not recovering by the end of each day was used as input) and censoring at day 21 (hour 504). Assuming that up to 12% of subjects will have incomplete data, we arrive at a sample size of 600 subjects in total, 300 per treatment group to yield at least approximately 530 with complete data (all 600 subjects will be included in the primary analysis with subjects with incomplete data censored as of their last entry).

Based upon these calculations, the study will enroll at least 600 subjects with laboratory-confirmed EV/RV infection up to a maximum of 700 subjects with laboratory-confirmed EV/RV infection. We estimate that this will require enrollment of up to 1,750 subjects in total assuming an EV/RV-positive rate of at least 40%.

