8.4.2. Population Pharmacokinetics Analysis

On Day 3, the plasma samples will be collected before the morning dose (at the trough). These data will allow for analysis of relationships between trough plasma concentrations and clinical and virologic response.

Day 3 trough plasma concentrations of tizoxanide and tizoxanide glucuronide will be summarized descriptively for each of the treatment groups. Exploratory analyses will be conducted to evaluate the relationships between plasma concentrations and age, race, gender, body weight, body mass index, concomitant medications, changes in viral titer over time, time from first dose to Symptom Response and adverse events.

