**Table 2: Definition of Analysis Populations**

Table Analysis Population	Definition
Intent to Treat (ITT)	All subjects who receive at least one dose of study medication
Intent to Treat Infected (ITI)	The subset of the ITT population who are positive for EV/RV by RT-PCR at any of the Baseline, Day 2 or Day 3 visits
Per Protocol	The subset of the ITI population with no major protocol deviations that may have an effect on the integrity of the data or the evaluation of effectiveness

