#### Analysis

Plasma concentrations of T and TG will be summarized descriptively for both treatment groups. Exploratory analyses will be conducted to evaluate relationships between plasma concentrations and age, race, gender, body weight, body mass index, concomitant medications (yes/no), changes in viral titer over time, Time to Symptom Response, and adverse events (yes/no). For continuous factors, the relationship with plasma concentrations will be assessed by Spearman's correlation analysis and Pearson's correlation analysis. For categorical factors, plasma concentrations will be compared among groups using the Kruskal-Wallis test.

Analysis Population(s): ITTI, NTZ-treated only

Derived Variables: Concomitant medication use: if any concomitant medication is used, then "yes", otherwise "no"

Adverse events: if any adverse event is reported, then "yes", otherwise "no"

Changes in viral titer over time: see [Section 11.5.5](#)

Time to Symptom Response: see [Section 11.2](#)

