16.2.8.2	Listing of Serum Biochemistry Laboratory Results	Listing	ITT
16.2.8.3	Listing of Urinalysis Laboratory Results	Listing	ITT
16.2.8.4	Listing of Plasma Tizoxanide and Tizoxanide Glucuronide Results	Listing	ITT
16.2.9.1	Listing of Vital Signs Data	Listing	ITT
16.2.9.2	Listing of Physical Examination Data	Listing	ITT

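### SAP 11.6.1 confines all plasma-concentration analyses to EV/RV-positive NTZ subjects, including those that do not depend on infection (demographics, concomitant medication, adverse events)

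*SAP*

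**What the plan says.** SAP 11.6.1 relates Day 3 tizoxanide and tizoxanide glucuronide concentrations to nine factors: age, race, gender, weight, BMI, concomitant medication, change in viral titer, Time to Symptom Response and adverse events. One population line governs all nine: "Analysis Population(s): ITTI, NTZ-treated only". SAP Table 2 defines ITTI as "The subset of the ITT population who are positive for EV/RV by RT-PCR at any of the Baseline, Day 2 or Day 3 visits". Display 14.2.13 in SAP Appendix 2 also carries ITTI, and no ITT version of that table is planned.

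The surrounding text is broader:

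- Protocol 5.5 plans the Day 3 visit and blood sample for each subject, with an opt-out for practical reasons but no condition on EV/RV status.
- Protocol 8.4.2 sets out the same programme ("Exploratory analyses will be conducted to evaluate the relationships between plasma concentrations and age, race, gender, body weight, body mass index, concomitant medications", then titer, response and adverse events) and names no infected subset. The ITTI restriction appears in 8.4.1, for efficacy.
- Protocol 8.4.3 evaluates safety in all randomized subjects who receive study medication, and SAP 12.1 bases safety tables on ITT unless otherwise stated.
- SAP Table 16 places plasma results among the safety listings, and listing 16.2.8.4, "Listing of Plasma Tizoxanide and Tizoxanide Glucuronide Results", is for ITT.

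**The concern.** Seven of the nine factors have no evident link to which virus caused the cold. All subjects meet the same clinical entry criteria and, within the NTZ arm, take the same regimen. Whether trough levels vary with weight, or whether subjects with higher levels report more adverse events, can be asked of an EV/RV-negative subject as well as a positive one. Exposure against adverse events is in substance a safety question, yet it is run in a subset defined for efficacy.

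These are the only planned analyses that relate concentration to body size, age or tolerability under one fixed regimen, in a trial that admits subjects from age 12 with no weight limit. Leaving out usable levels widens the uncertainty for no evident gain in validity, and a weak null result in the smaller set could be read as more reassuring than it is.

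**Working it through.** **Inputs**

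- Enrolment and positive rate, protocol 8.1: "enrollment of up to 1,750 subjects in total assuming an EV/RV-positive rate of at least 40" percent.
- Target, protocol 8.1: "the study will enroll at least 600 subjects with laboratory-confirmed EV/RV infection up to a maximum of 700 subjects".
- Allocation 1:1, protocol section 3.
- Day 3 attendance of at least 75% of enrolled subjects, protocol 5.5.
- Assumption of this check: Day 3 attendance does not depend on infection status.

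**The plan's own figure.** Total enrolled = positives / positive rate = 700 / 0.40 = 1,750, as the protocol states.

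**Levels available and used.** NTZ levels in ITT = (enrolled / 2) × 0.75. Levels in ITTI = that number × positive rate.

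| Enrolled | Positive | Rate | NTZ levels, ITT | Used (ITTI) | Left out |
|---|---|---|---|---|---|
| 1,750 | 700 | 40% | 656 | 262 | 60% |
| 1,500 | 600 | 40% | 562 | 225 | 60% |
| 1,400 | 700 | 50% | 525 | 262 | 50% |
| 933 | 700 | 75% | 350 | 262 | 25% |

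The 50% and 75% rows are illustrative. Because the protocol assumes a rate of at least 40%, 60% is the planned maximum. It would be exceeded only if that assumption failed; for example, 600 positives among 1,750 would leave out 1 − 600/1,750 = 66%.

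**Is the independence assumption safe?** ITTI also admits subjects first positive on Day 2 or 3, so attenders are slightly more likely to be in it. If those visits add x to the positive rate among attenders and the overall rate stays at 40%, the attenders' rate is 0.40 + 0.25x. With x between 0.02 and 0.06 this is 40.5% to 41.5%, so 59.5% to 58.5% are left out. The result barely moves.

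**Precision for continuous factors (age, weight, BMI).** The standard error of Fisher's z is 1/√(n − 3), and the correlation detectable with 80% power at two-sided 0.05 is tanh(2.80 × SE).

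- n = 262: SE = 1/√259 = 0.062, detectable r ≈ 0.17.
- n = 656: SE = 1/√653 = 0.039, detectable r ≈ 0.11.
- n = 350 (all ITT levels at a 75% rate): detectable r ≈ 0.15.

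At the 40% rate the standard error is therefore about 37% smaller with all levels (0.039/0.062 ≈ 0.63).

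**Adverse-event relation.** The SAP uses a Kruskal-Wallis test here, so the correlations above do not apply directly. With the same proportion of subjects in each group, precision still scales roughly as 1/√n. The ratio √(262/656) = 0.63 gives a similar gain.

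As a scale for one event, protocol section 3 gives diarrhea rates of 8.1% on NTZ and 5.8% on placebo. Expected cases are 0.081 × 262 = 21 against 0.081 × 656 = 53. The part above the placebo rate is only 0.023 × 262 = 6 against 0.023 × 656 = 15.

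**The case against.** The best defence is purpose. Protocol section 2, protocol 8.4.2 and SAP 8.2 each describe the concentrations as serving the relation with clinical or virologic response, and those relations need infected subjects. Protocol 8.4.2 names no population and protocol 8.4 leaves detail to the SAP, so the SAP contradicts nothing. The section is exploratory and carries no alpha. This stands as a reason to keep ITTI for titer and symptom response, and as a limit on the consequence. It does not explain why an exposure-safety relation should be run in an efficacy subset.

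Three further points stand in part:

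- Protocol section 3 already reports similar pharmacokinetics and safety at ages 12 to 17 and 18 to 65, from a 500 mg tablet. That eases the age question but not weight, BMI or adverse events.
- The gain for continuous factors is from about 3% to about 1.2% of shared variance (0.172² and 0.109²). A large weight effect would show with 262 subjects.
- No passage states that samples from EV/RV-negative subjects will be assayed. The ITT label on listing 16.2.8.4 implies it but does not establish it.

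Stronger readings are tempting and go too far. A reader might say that 60% of the concentrations are discarded. They are omitted from the analysis but still listed for ITT, and 60% is a planning ceiling. A reader might also take "Studies of NTZ at higher doses have shown dose-dependent increases in the frequency of reported diarrhea and other gastrointestinal side effects" to make diarrhea the one expected signal, buried by the pooled adverse-event factor. Protocol Table 9 shows another: chromaturia, at 5.2% on NTZ against 0.4% on placebo. Most of the expected diarrhea cases, 5.8/8.1 or about 72%, are background at the placebo rate.

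**Conclusion.** The point holds as a matter of efficiency and fit. For seven of the nine factors the ITTI restriction gives up precision with no evident protection against bias, and it is out of line with how the SAP treats safety elsewhere. At the planning figures, up to about 60% of NTZ levels are left out of those relations, with a detectable correlation of about 0.17 instead of 0.11. The share falls to 50% or 25% if the positive rate is 50% or 75%; the documents give no observed rate.

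The size rests on 1:1 allocation, 75% Day 3 attendance unrelated to infection, and assay of samples from EV/RV-negative subjects. No power was calculated for the adverse-event test itself, so the documents do not support saying that a real exposure-tolerability relation would be missed, only that it would be estimated less precisely than the planned samples allow. The primary and secondary analyses are untouched. The change is worth making before unblinding but is not critical.

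**What to change.** In SAP 11.6.1, replace the single population line with two:

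1. All NTZ-treated ITT subjects with a Day 3 concentration, for age, race, gender, weight, BMI, concomitant medication and adverse events.
2. NTZ-treated ITTI subjects with a Day 3 concentration, for change in viral titer and Time to Symptom Response.

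Align display 14.2.13, and state that Day 3 samples are assayed whatever the EV/RV result. The cost is SAP wording and two denominators in one exploratory table. No new samples are needed if the assays are done as listing 16.2.8.4 implies. SAP 11.6.2 to 11.6.4 already use both ITTI and ITT.

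Optionally, add gastrointestinal events, diarrhea and chromaturia as separate yes/no factors beside the pooled adverse-event factor. This is a preference: the pooled factor does implement protocol 8.4.2.

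Two slips in SAP 11.6.1 can be corrected in the same edit. It promises concentration summaries for both treatment groups while limiting the population to NTZ, and it points to 11.5.5 for the change in viral titer, which is in 11.5.4.

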5.5. Day 2 and 3 Evaluations

A study physician, nurse or other study personnel will visit each subject at home (or at the clinic or another location as agreed with the subject) on each of Days 2 and 3 to (i) collect two nasopharyngeal swabs for detecting and quantifying EV/RV, and (ii) screen for potential complications and adverse events. Subjects will be referred for immediate care as needed based on the screening. All information gained from these visits will be included in the case report forms for each subject. In addition, a blood sample for pharmacokinetics will be collected on Day 3. The Day 2 and Day 3 visits will occur at approximately the same time of day that the patient took his/her first dose of study medication (approximately 24 and 48 hours after the first dose). On Day 3, the blood sample for pharmacokinetics will be collected before the first dose of that day.

Study sites or subjects may opt out of these Day 2 and Day 3 visits due to site staffing, subject availability or other practical considerations or preferences; nevertheless at least 75% of subjects enrolled in the trial are expected to complete the Day 2 and Day 3 visits and related procedures (for viral kinetics and pharmacokinetics).

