5.7. Day 22 Follow-up (+3 days)

Subjects will return to the clinic on Day 22, and the following procedures will be performed:

1. Brief physical examination (body weight and vital signs with nursing physical assessment) including symptom directed physician physical examination as required by subject symptoms. Vital signs will include blood pressure, pulse, respiratory rate and oral temperature (use standard electronic oral thermometer provided by Sponsor).
2. Collection of two nasopharyngeal swabs using nylon flocked dry swabs (Copan Diagnostics) for RT-PCR and culture (to be tested for presence of virus only if the sample collected at the preceding time point had detectable virus).
3. Review and recording of concomitant medications.
4. Review and recording of adverse events/side effects and complications. Note that all adverse events and complications must be followed until their resolution or stabilization even beyond the 22-day study period.

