10. ADVERSE EVENTS

The term “adverse event” is defined for purposes of this study as any unwanted physical, psychological or behavioral change experienced by a subject during the course of the study and after taking the first dose of study medication regardless of its severity or relation to the study. Adverse events may include symptoms, signs, unexpected worsening of pre-existing conditions, clinically significant changes in laboratory values, diseases and syndromes, and significant and unexpected failures of pharmacological action of other medications. Symptoms of colds due to EV/RV infection (cough, sore throat, nasal obstruction, fatigue, headache, myalgia, feverishness) and complications of colds will not be reported as adverse events.

Adverse events will be recorded on the appropriate EDC forms throughout the study, and the severity of each adverse event will be graded on a four-point scale: mild, moderate, severe, or life-threatening ([See Appendix II](#)). The duration of the adverse event and relationship to the study drug will also be recorded. All adverse events must be followed until their resolution or stabilization even beyond the planned study period.

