## 8.2. Study Design

The study will be a multicenter, randomized, double-blind trial to evaluate the efficacy of NTZ compared to placebo in treating colds due to EV/RV infection. Subjects will be selected according to the inclusion and exclusion criteria listed in the protocol.

Immediately after completion of informed consent, screening, and enrollment in the study, two Baseline nasopharyngeal swabs will be collected for RT-PCR. Blood and urine samples will be collected for laboratory safety tests. Subjects will receive instruction on completing their electronic diaries, recording concomitant medications and attending follow-up visits.

Subjects will be randomized 1:1 to one of the following groups:

- Group 1 (NTZ): Two NTZ 300 mg tablets b.i.d. for 5 days
- Group 2 (Placebo): Two placebo tablets b.i.d. for 5 days

Randomization will be stratified by (1) time from onset of illness to time of first dose of study medication (0-24, >24-≤36, or >36 hours from onset), (2) pre-enrollment use of symptom relief medication, and (3) presence of underlying lung condition including asthma, COPD, or past or present history of smoking.

Study medication will be taken in the morning and evening with food. The first dose will be taken with food in the physician's office under the observation of the Principal Investigator or a member of the Investigator's staff. The second dose will be taken by the patient as close as possible to 12 hours after the first dose.

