#### 10.1.5. Prior and Concomitant Medication

The prior and concomitant medication tables will summarize the number and percentage of subjects receiving each medication by Level 4 Anatomical Therapeutic Chemical (ATC) classification and standardized medical name.

Analysis Population(s): ITT, ITTI

Derived Variables: Prior medication classification = medications with stop dates prior to screening date

Concomitant medication classification = medications with administration occurring on or after the date of the first administration of study drug until the end of the study

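### In the exploratory pharmacokinetic analysis, the any-time flags for concomitant medication and adverse events may dilute a true relationship with the Day 3 trough

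*SAP*

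**What the plan says.** Protocol 5.5 schedules a single pharmacokinetic sample: "On Day 3, the blood sample for pharmacokinetics will be collected before the first dose of that day". The visit is set at about 48 hours after the first dose. Treatment is short; SAP 8.2 gives "Group 1 (NTZ): Two NTZ 300 mg tablets b.i.d. for 5 days".

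SAP 11.6.1 relates the tizoxanide and tizoxanide glucuronide concentrations to several factors in NTZ-treated subjects of the infected population (ITTI). Categorical factors are compared by the Kruskal-Wallis test. Two of them are yes/no flags: medication is yes "if any concomitant medication is used", and adverse events are yes "if any adverse event is reported". Neither derivation carries a time limit, and Protocol 8.4.2, which introduces the analysis, adds none.

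The periods come from elsewhere:

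- **Medication.** SAP 10.1.5 holds the only SAP definition of concomitant: "medications with administration occurring on or after the date of the first administration of study drug until the end of the study".
- **Adverse events.** Protocol Section 10 states: "Adverse events will be recorded on the appropriate EDC forms throughout the study".
- **Last visit.** Protocol 5.7 (Day 22, +3 days) still lists "Review and recording of concomitant medications" and "Review and recording of adverse events/side effects and complications".

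**The concern.** For co-medication, the flag lets the supposed cause follow the outcome. A subject who first takes a medicine on Day 10 is compared as a user on a concentration measured on Day 3. For adverse events the order in time is right but the window is too long: an event in the third week is set against a level from a five-day course that ended more than a week earlier.

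In both cases the yes group mixes subjects who could carry a signal with subjects who could not, and the contrast shrinks. The protocol lists the relationship between pharmacokinetics and response among its other important objectives, and 8.4.2 names concomitant medications and adverse events specifically. What is at stake is that a null result from these flags could be read as no interaction, or no link between exposure and safety, when the coding contributed to the null.

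**Working it through.** The documents give no sample size or power for this analysis, so there is no stated figure to reproduce. The check has three parts.

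**1. Timing.** Inputs: 10 doses 12 hours apart; sample at about hour 48; follow-up of 21 days (hour 504, SAP 8.3); mean Day 7 half-lives of 2.19 h (tizoxanide) and 4.99 h (glucuronide, SD 5.20 h) from Protocol Table 1.

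- Last dose: 9 × 12 = hour 108.
- Follow-up after the sample: (504 − 48)/504 = 456/504 = 90%.
- Five half-lives after the last dose: 108 + 5 × 2.19 = hour 119; 108 + 5 × 4.99 = hour 133.
- Follow-up after those points: (504 − 119)/504 = 76%; (504 − 133)/504 = 74%.
- Glucuronide at mean plus one SD: 4.99 + 5.20 = 10.19 h, and 108 + 5 × 10.19 = hour 159, which is on Day 7.

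These are shares of clock time, not of events or of medication starts.

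**2. Dilution for medication.** Let p be the share using a medication before the sample and e the share using one at any time. Everyone in p is also in e, so the no group stays clean and the yes group is a mixture. The expected difference is multiplied by p/e. Assumptions: 240 samples (80% of 300 per arm; the documents expect at least 75%, or 225), normal log concentration, true shift of 0.5 SD, two-sided 0.05, Kruskal-Wallis, simulated. Each power carries a simulation error of one to two points.

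| Before sample (p) | Ever (e) | Diluted shift, 0.5 × p/e | Power, windowed | Power, any-time |
|---|---|---|---|---|
| 20% | 25% | 0.40 SD | 85% | 73% |
| 30% | 35% | 0.43 SD | 93% | 86% |
| 40% | 45% | 0.44 SD | 96% | 92% |
| 20% | 40% | 0.25 SD | 85% | 44% |
| 40% | 60% | 0.33 SD | 95% | 68% |
| 20% | 60% | 0.17 SD | about 85% | 23% |

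**3. Dilution for adverse events.** A second simulation used 225 samples (0.75 × 300), a log-SD of √ln(1 + 1.01²) = 0.84 from the Day 3 tizoxanide CV of 101% (Protocol Table 2), and an assumed geometric mean ratio of 1.5 between subjects with and without an event around dosing.

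- 10% with an event around dosing: power is 56% with the window. It is 39%, 29% and 21% without it when 5%, 10% and 20% of the others have only a late event.
- 20% with an event around dosing: power is 80% with the window, and 70%, 62% and 46% without it.

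With no true effect, the any-time coding rejected in 5.6% of runs. The harm is attenuation, not false positives.

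**The case against.** The strongest reply is that little depends on this. The analysis is labelled exploratory, sits outside the testing hierarchy of SAP 11.4, and carries no power claim. Medication dates, adverse-event dates and concentrations are all listed, so a windowed version can be run later. That stands, and it sets the severity.

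The size is also open. Protocol 9.6 continues medicines for pre-existing conditions, so those are already in use on Day 3. It disallows most cold remedies, leaving acetaminophen and dextromethorphan. Enrolment is within 40 hours of onset, and the protocol's challenge-study summary puts the symptom peak about 24 to 48 hours after symptoms begin, so symptom-driven use should start early. Late-only use may then be small, as in the first three rows of the table. Late use remains possible: the diary runs through Day 21, and secondary infections needing systemic antibiotics are among the complications tracked. For adverse events, cold symptoms and complications are not to be reported as such (Protocol Section 10), which removes one source of late events.

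Two further limits stand. The simulations assume that any medication, whatever its class, shifts the concentration; a real interaction confined to a few drugs would be diluted by pooling even with a perfect window. And events after Day 3 but during dosing are properly related to exposure, since the protocol reports steady state by Day 2.

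A reader might infer that the flags mask any real interaction or exposure-safety link. The documents do not support that. They give no rates of late-only use or late-only events, and at the mild end most of the power remains.

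**Conclusion.** The point holds as a possible dilution in an exploratory analysis. The stated derivations count subjects as users when their medication began after the sample, and count adverse events with onset long after five mean half-lives have passed. No other section narrows either flag.

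Under the assumed 0.5 SD shift, the loss of power for co-medication runs from 4 points (96% to 92%) to about 62 points (about 85% to 23%). It rests on the share of late-only users, which is unknown. The adverse-event figures rest on an assumed ratio of 1.5 and assumed event rates. Neither set predicts what this trial will show. Primary and secondary conclusions are untouched. Severity is low.

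**What to change.** In SAP 11.6.1:

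- Code concomitant medication yes only if taken between the first dose and the Day 3 draw, or ongoing at the draw.
- Code adverse events yes only if onset lies between the first dose and the Day 7 (±1) visit. A cut-off of about 24 hours after the last dose (108 + 24 = hour 132) would be too early. The only scheduled post-baseline safety laboratory draw is at that visit, nominally hour 144, and clinically significant laboratory changes are adverse events under Protocol Section 10. The Day 7 bound also allows for the wide spread in glucuronide half-life.
- Apply the date rules of SAP Table 4 and say how a wholly missing medication start date is treated, because Table 4 leaves it unimputed. Note two effects: a partial medication start date goes to the first of the month or 1 January and may fall before the draw, and a wholly missing adverse-event onset becomes the first-dose date and so falls inside the window.
- Keep the any-time versions as secondary.

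The data are already planned: ingestion times in the diary (Protocol 5.10), medication start and stop dates (SAP Table 5) and adverse-event onset dates (SAP Table 16). The cost is fewer yes subjects in each comparison and a little more derivation work.
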